
Rationale for carrying out the trial:

In order to achieve patient satisfaction and shortest treatment duration, there is no gold standard guidelines which technique achieves the most efficient results at the shortest period of time of retraction. The first premolars are usually the main choice of extraction in bimaxillary protrusion cases, maximum anchorage of the posterior teeth become of great importance for two reasons; first to retract the anterior teeth to their greatest extent and second to increase the chances of correcting the profile maximum retraction of anterior teeth into the extraction space and retraction is the ideal treatment choice. (2,3)

Space closure can be achieved by two methods either the two-steps (4) or by en-masse technique. A debate was raised between the two methods regarding friction mechanics.

It has been recommended that two steps techniques would provide less load on the posterior teeth thus minimal anchorage loss but on the other hand, separate canine retraction followed by incisors retraction would take longer time than closing it in a single step and it is aesthetically unacceptable (5) for some patient as there is a space after canine retraction and it persists up until the full retraction of anterior segment, for these reasons en-masse retraction is expected to be superior treatment option as retraction will be done by one step (6).

Nowadays, Orthodontists prefer using the en-masse technique because of its simplicity and the extraction space will be closed in one step so better aesthetics. But theoretically this technique may provide more loads on posterior segment so more risk of anchorage loss.

In general orthodontic treatment takes long time especially in extraction cases by average two years treatment time (7). So the longer treatment duration, the greater risks on the dentition by a way of root resorption (8), periodontal disease and enamel decalcifications (9). Thus, reduction of the treatment duration is of prime concern to both the patient as well as the orthodontist.

For many years, practitioners have been looking for an efficient force system that can close extraction spaces quickly, aesthetically, accurately, and effectively. It was determined that both were effective methods for retraction (10). However, there is no evidence which technique offers shorter treatment duration with best retraction and space closure.

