6. Minimal crowding 2-3 mm.

Exclusion Criteria: for the involved subjects included:

1. Patients suffering from any systemic diseases interfering with tooth movement.
2. Patients with extracted or missing permanent teeth. (Except for third molars).
3. Patients with badly decayed teeth.
4. Patients with any parafunctional habits (i.e. Bruxism, tongue thrusting, mouth breathing, etc...).
5. Patients with previous orthodontic treatment.

C] Interventions:

➤ Medical History Questionnaire:

For every patient, to exclude the presence of any systemic condition interfering with orthodontic treatment.

➤ Clinical Examination:

Oral structures will be examined to identify caries, fracture or missing teeth. Gingival tissues will be carefully examined for any gingivitis, periodontitis, recession, or lesions.

➤ Diagnosis

Check the potential patient to fulfill the previously mentioned inclusion criteria. Every participant will be asked to sign an informed consent about the study. Full set of records (study models, panorama radiograph and lateral cephalometric radiographs, photos) will be taken for every patient as part of the routine procedure for treatment of patients in the clinic of the Orthodontic Department, Future University in Egypt.

➤ Clinical Procedure:

After taking pre-treatment records, every patient will receive:

- Miniscrews will then be placed in the upper arch between the second premolar and first molar.
- The patient will be referred for extraction of first premolars.

- Anchorage will be secured, followed by Leveling and alignment for the bonded and banded teeth through following the wire sequence: 0.014 NiTi, 0.016×0.022 NiTi and 0.017×0.025 StSt.
- Bonding of all teeth except for first premolars and banding/bonding the first and second molars will be done using Roth prescription brackets (0.022 x 0.028 slot)*.
- After leveling and aligning is completed (right before retraction), the patient will be referred for the uptake of pre-intervention records for en masse group (Impression for models, photos extra oral and intra oral and pain questionnaire).
- For two step group canine retraction will take place on a 0.017×0.025 StSt arch wire, once canine retraction stage is completed, the patient will be referred for the uptake of pre-intervention records.

➤ **Acquisition of pre-intervention records:**

- Alginate impressions will be taken before retraction (without the arch wire in place) followed by digital scanning of produced models.

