- Photos (Extra and intra oral).
- Pain questionnaire distributed with explanatory session on it.

➤ **Begin of Retraction:**

- Crimpable hooks added to the arch wire (0.017"x0.025" Stainless steel) distal to the lateral incisor passing near the center of resistance of the anterior segment.
- A ligature wire extending between the second premolar and miniscrews will be used for proper anchorage control.

- Retraction will start on a 0.017"x0.025" Stainless steel wire using elastomeric chain (force applied will be 200 g per side) (24) extending between the crimpable hooks and the molar hooks.
- The force will be measured by a force gauge and reactivated every 4 weeks maintaining constant force of retraction all over the retraction phase.

➤ **Follow up visits**

Patients will be asked to attend for follow up sessions every 4 weeks for:

- Evaluation of miniscrews stability.
- Replacement of the power chain to maintain a force of 200 gm per side for en masse group and 160 gm per side for two step group.
- Impression taking to assesses amount of space closure.
- Recording the pain scoring sheet.

➤ **Criteria for discontinuing or modifying the allocated intervention:**

In cases of prolonged swelling or pain related to the miniscrew, the patient will be given strict oral hygiene measures and may wait for three weeks before the beginning of retraction.

In cases of loose or broken miniscrews, the screw will be removed and replace the miniscrew after total resolution of the inflammation.

In case of non compliant patients.

□ **Post-retraction Questionnaire:**

The patients of both groups will be asked to fill in questionnaires regarding their experience with their allocated technique, during the whole retraction period from day of extraction till the end of retraction.

□ **Retraction records**

Following en-masse and two steps retraction, patients will be referred to the same radiology center to acquire the final cone-beam CT to assess the movement and inclination of anterior teeth.

The final dental model will be used to assess the rate of retraction and molar anchorage loss achieved throughout the study.

□ **Criteria of ending the retraction**

- Class I canine relation
- Normal overjet
- Balanced facial profile
- Closing extraction space

□ **Material Used**

- American Orthodontics Brackets, Roth prescription, 22 slot size.
- American Orthodontics Elastomeric power chains
- American Orthodontics Elastomeric O-ties
- American Orthodontics Ligature wire.

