- Miniscrew, 8 mm length x 1.6mm diameter TAD (Jeil).
- American Orthodontics Arch wires.
- American Orthodontics Molar bands/tubes.

D] Outcomes

[figure not shown]
Primary outcome: is to monitor the Duration of space closure during en-masse and two steps retraction. All outcomes will be assessed as the difference between T0 at the start of retraction and T1 after complete space closure.

Secondary outcomes: is to monitor the changes in the anterior teeth position (final anterior teeth tip, torque and vertical position), anchorage loss, presence of any root resorption and pain associated with the different methods used for retraction.

E] Participant timeline:

1. The principle investigator will screen the potential patients through careful clinical examination of patients at the orthodontic department, Faculty of Oral and Dental Medicine, Future University in Egypt.
2. All recruited patients should fulfil the previously mentioned inclusion and exclusion criteria.
3. Every participant will be asked to sign an informed consent before the beginning of the study.
4. After patient's enrolment, each participant will be asked for pre-intervention records to ensure proper diagnosis.
5. The principle investigator will randomly allocate the patients to one of the intervention groups.

6. Anchorage will be secured by placement of miniscrew, followed by extraction of the first premolar.
7. Active intervention will begin after proper levelling and alignment of the upper arch.
8. The principle investigator will take pre-retraction records for every participant T0.
9. Power chain is used for anterior segment retraction.
10. Each patient will come every 4 weeks for follow up visit, for appliance activation and uptake of impression for interim records + monitoring of recording the VAS sheet.
11. After complete space closure, the principle investigator will take post-retraction records for each participant T1.
12. Every patient will fill up a questionnaire regarding his experience during treatment.
13. The principle investigator will continue the normal treatment and achieve proper finishing for every patient after the end of the study.

F] Sample size calculation:

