- The specialized statistician will be responsible for the statistical analysis of the study by:
 1. Presenting the data as mean, standard deviation (SD) and Standard error (SE) values.
 2. Using Paired t-test to compare between the friction and the frictionless group of retraction as well as to compare between the pre-and post -treatment data for each group.
 3. Using Anova test to determine the rate of anterior segment retraction.
 4. Statistically evaluate the patient acceptance for both techniques.
- For this study, the specialized statistician will use IBM11 SPSS12 Statistics Version 20 for Windows to perform the required statistics.
- The significance level will be $P \leq 0.05$. Highly significant variables are detected when P value is less than 0.01.

Assessors Reliability:

- To achieve high reliability for measurements, the supervisor will choose a well-experienced inter-examiner during the study.
- A training session will be provided for the examiners to ensure standard measurements techniques.
- Each examiner will complete the measurements on a model and will repeat the procedure after one week to assess the intra- and inter-examiner reliability.
- The supervisor will compare the measurements of the two assessors for disagreement with a difference of more than one millimeter.
- The supervisor will evaluate the amount of variation in measurements among and between examiners to test the performance of each assessor.
- The examiner with less reliability will receive additional training but will be replaced during the study.
- The specialized statistician will calibrate the intra and inter-examiner reliability for the measurements of the study by the Intra-class correlation coefficient (ICC). The closer the ICC to 1.0, the higher reliability between assessors. According to Fleiss:" ICC values between 0.7 and 0.9 represent good reliability." The kappa scores between study examiners will be calculated, a range of 0.60-0.80 will represent acceptable reliability.

IV) Method Monitoring:

A] Data Monitoring: An independent Data Monitoring Committee (DMC) will monitor the results of the study. The Committee will include the trial's supervisors, who will periodically review the trial data and identify the need for any adjustments or modifications during the study.

B] Interim Analysis: no interim analysis will be performed during the study.

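### If two-step baseline records are taken after canine retraction, the planned anterior retraction rate omits the canine months in that arm only and is not comparable between arms

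*Combined protocol and SAP*

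**What the plan says.** The analysis of the rate is one line, Statistical Analysis (III C), item 3: "Using Anova test to determine the rate of anterior segment retraction". It names no landmark, start date, denominator or grouping factor. The Retraction records paragraph adds only the data source: "The final dental model will be used to assess the rate of retraction and molar anchorage loss achieved throughout the study".

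The start of measurement is described in two ways.

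- Clinical Procedure (I C), en-masse arm: "After leveling and aligning is completed (right before retraction), the patient will be referred for the uptake of pre-intervention records for en masse group".
- Clinical Procedure (I C), two-step arm: the canines are retracted first and, "once canine retraction stage is completed, the patient will be referred for the uptake of pre-intervention records".
- Outcomes (I D): "All outcomes will be assessed as the difference between T0 at the start of retraction and T1 after complete space closure".
- Participant timeline (I E), step 8: "The principle investigator will take pre-retraction records for every participant T0". Step 9 follows directly: "Power chain is used for anterior segment retraction".

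The Rationale states the expectation for total time: "separate canine retraction followed by incisors retraction would take longer time than closing it in a single step". Rate appears neither in the outcome table of the PICOS section nor among the outcomes listed in I D.

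**The concern.** A rate is a distance over a time, and the two arms are compared fairly only if both parts are measured the same way. Under the Clinical Procedure, the en-masse patient enters the measured period with all six anterior teeth still to be moved, and the whole of retraction is counted. The two-step patient enters it with the canines already back, and only the incisor stage is counted. The months spent on the canines are retraction time, yet they would be missing from the denominator in one arm only.

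The trial asks which technique is shorter. A rate that leaves out one stage of one technique can make that technique look faster than it is, and in some circumstances faster than a technique that finishes sooner. The cause is the record-timing rule, not treatment.

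**Working it through.** The plan states no figure for the rate, so there is none to reproduce. The sample-size inputs (SD 0.76, difference 1.0, no unit given) do not enter. All distances and durations below are assumptions.

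**1. The measured window in each arm, if the Clinical Procedure is followed**

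- En-masse: before any retraction to T1, six teeth moving together.
- Two-step: end of the canine stage to T1, incisors only.

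**2. Size of the distortion.** Let D be the incisor distance, t1 the en-masse retraction time, tc the canine stage and t2 the incisor stage, with f = tc/(tc + t2).

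- Two-step rate on the late start: D/t2.
- Two-step rate over all retraction: D/(tc + t2).
- Ratio: (tc + t2)/t2 = 1/(1 − f). This gives 1.5 at f = 1/3, 2 at f = 1/2 and 3 at f = 2/3.

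**3. An example in which the ranking reverses.** Assume D = 5 mm in both arms, en-masse 7 months, two-step 8 months, f = 1/2 (so tc = t2 = 4).

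- En-masse: 5/7 = 0.71 mm/month.
- Two-step, late start: 5/4 = 1.25 mm/month, a ratio of 7/4 = 1.75, so 75% faster in appearance.
- Two-step, all months: 5/8 = 0.625 mm/month, a ratio of 7/8 = 0.875, so 12.5% slower.

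**4. When it reverses.** With equal D, two-step has the higher late-start rate when t2 < t1, and takes longer overall when tc + t2 > t1. Reversal therefore needs t1 − tc < t2 < t1.

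Over t1 = 6, 8 or 10 months, tc = 3 or 5 months and t2 = 0.6, 0.8 or 1.0 of t1, there are 3 × 2 × 3 = 18 combinations:

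- 10 reverse;
- 6 (those with t2 = t1) give tied rates although two-step takes longer;
- 2 (t1 = 8 or 10, tc = 3, t2 = 0.6 × t1) have two-step truly shorter.

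**5. An example in which it does not reverse.** Two-step 8 months, en-masse 5, f = 1/3: t2 = 8 × 2/3 = 5.33 months, longer than 5. With D = 5 mm the late-start rate is 5/5.33 = 0.94 against 1.00 mm/month. The order is right, but the true gap (0.625 against 1.00) is mostly hidden.

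**6. Dependence on distance.** Two-step 6 months, en-masse 5, f = 1/3 gives t2 = 4. With 5 mm in both arms the late-start rates are 1.25 and 1.00, an apparent 25% advantage. With 4 mm in the two-step arm they are 4/4 and 5/5, and the advantage is gone.

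**7. The primary outcome on the same clock.** In the example of step 3, duration from the late T0 to T1 would be 4 months for two-step against 7 for en-masse. Duration and rate would then both favour two-step.

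**8. A common start.** Counting from the first retraction force in both arms gives D/t1 and D/(tc + t2). With equal D these rank the arms as total duration does.

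**The case against.** The strongest reply is that this is the T0 problem seen through a secondary analysis. That stands: every figure above comes from the late start in the two-step arm, and a common start removes the distortion. What the T0 correction alone does not supply is a definition of the rate, meaning which teeth and which months.

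A second reply is that the text does not clearly fix a second-stage rate. The Outcomes section and timeline step 8 can be read as including the canine stage, the Data collection section names the primary outcome as a total duration with monthly models for every participant, and the follow-up list does not confine visits to the second stage. This also stands, as a contradiction to be reconciled. The Clinical Procedure remains an explicit rule for when the two-step records are taken.

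Third, item 3 speaks of determining a rate, not of comparing arms. An ANOVA across monthly models within an arm is possible. A between-arm contrast is a natural reading in a two-arm trial, but it is inferred.

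Finally, the proposed rate includes canine-stage months in which the incisors are not being retracted. That is deliberate: it describes the whole of retraction in both arms. The price is that, for equal distances, it ranks the arms as duration does.

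**Conclusion.** The concern holds in a conditional form. If the Clinical Procedure governs the baseline, the anterior retraction rate covers different teeth and a different part of treatment in each arm. For a given incisor distance, the two-step value overstates its whole-retraction rate by 1/(1 − f), that is 1.5-fold at f = 1/3 and 2-fold at f = 1/2. The documents do not give f. With equal distances, a between-arm comparison would rank two-step first although it takes longer overall whenever its second stage alone is shorter than en-masse retraction.

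Three stronger conclusions might be inferred, and the documents do not support them.

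- *The ranking will be reversed.* With en-masse fixed one month shorter, two-step durations T of 6 to 10 months and f from 1/3 to 2/3, the apparent two-step advantage runs from 25% to 170%. That grid builds the result in: reversal there needs only f > 1/T, and every f used exceeds the largest 1/T of 1/6. The documents give no durations or distances, and steps 5 and 6 of the working show cases without reversal.
- *The rate will contradict the primary outcome.* That needs T0 corrected for duration but not for rate. Under the Outcomes section both run from T0 to T1, so both would lose the canine months.
- *This is a separate fault from the T0 mismatch.* The cause is the same, and its effect on the primary duration matters more.

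Since rate is not a listed outcome, this should be corrected but does not by itself undermine the trial.

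**What to change.** 1. Reconcile the Clinical Procedure (I C) with the Outcomes section (I D) and timeline step 8 (I E), so that the pre-retraction model is taken before the first retraction force in both arms. In the two-step arm that means before the canine stage.
2. In Statistical Analysis item 3, define one rate per patient: the distance moved by the same incisor landmark from that model to T1, divided by all months from the first retraction force to T1. Carry the same definition into the Retraction records paragraph.
3. Name the contrast: en-masse against two-step, one value per patient, with an independent-samples test.
4. Report the canine-stage and incisor-stage rates of the two-step arm descriptively.

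This is more than a change of wording. If no pre-canine model is currently taken, it costs one impression per two-step patient, although timeline step 8 already implies one. It has to be settled before canine retraction starts, because a missed model cannot be recovered. The other small cost is that, for equal distances, the rate adds little to total duration as a comparison of the arms.

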Assignment to either intervention will occur before levelling and alignment stage.

D] Blinding:

Blinding of the operators: Blinding will not be possible for the operators during the application interventions and during the follow up visits. The principal operator is responsible for assigning subjects to interventions according to the concealed allocation, appliance activation at follow up visits, dental impressions and acquisition of dental casts.

Blinding of the outcome assessors: It is a single blinded study, therefore, only the outcome assessors will be blind. The patients name will be sealed from pre and

post radiographs and study models. Then two assessors will carry out, blindly and independently, the measurements and analysis of the study.

III) Data collection, management and analysis:

A] Data collection methods:

Primary outcomes:

1. Total Retraction Duration: to assess the timing of antero-posterior movement of anterior teeth and first molars, the principle investigator will take study models for every participant monthly during the follow up visits. Then will digitize the models and identify the landmarks, reference lines and planes on the pre, interim and post-retraction digital dental models for measurements reading. Also, by identifying the landmarks, reference lines and planes using CBCT taken before and after the completion of retraction.

Secondary outcome:

1. Anchorage loss: will be accessed by the principal investigator via CBCT taken before and after the completion of retraction by identifying the landmarks, reference lines and planes, then will interpret the measurements in degrees and millimeters.

2. Pain: Each patient will fill a questionnaire regarding his treatment experience in a VAS scoring from 1-10. The questionnaire will include several questions related to oral hygiene, pain and discomfort experienced throughout the trial.

B] Data management:

A colleague outside the research team will enter the data and organize it in excel sheets in the computer of the orthodontic department.

Data will include all photographs, models, radiographs and filled questionnaire.

C] Statistical Analysis:

- The principle investigator will be responsible for the extraction of the required data from the CBCT taken before and after retraction as well as the study models taken at every follow up visit. The data will be sent to a specialized statistician.

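### The ANOVA for rate of retraction has no stated type or unit of analysis; pooling the repeated monthly models as independent would inflate the between-arm error

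*Combined protocol and SAP*

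**What the plan says.** The only analysis instruction for rate is item 3 of the list in III) C] Statistical Analysis: "Using Anova test to determine the rate of anterior segment retraction". Item 2 of that list separately assigns a t-test to the comparison between groups and to the pre/post comparison.

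Repeated measurement is documented in several places. In III) A] Data collection methods, under total retraction duration, "the principle investigator will take study models for every participant monthly during the follow up visits", and landmarks are then identified with "reference lines and planes on the pre, interim and post-retraction digital dental models for measurements reading". The data extracted for the statistician cover CBCT "as well as the study models taken at every follow up visit". The follow-up interval in C] Interventions is 4 weeks.

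Two other statements point to a single value per patient. Under Retraction records: "The final dental model will be used to assess the rate of retraction and molar anchorage loss achieved throughout the study". Under D] Outcomes: "All outcomes will be assessed as the difference between T0 at the start of retraction and T1 after complete space closure".

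Rate of retraction is not in the outcome table, nor among the primary and secondary outcomes listed in D] Outcomes. The primary outcome is duration of space closure.

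**The concern.** An ANOVA on several monthly values from each patient is a different test from an ANOVA on one rate per patient, and the plan does not say which is meant. The monthly reading is credible. With two arms and one rate each, ANOVA adds nothing to the t-test already in the list, so a separate ANOVA line makes most sense if the monthly values enter it.

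On that reading, nothing in the plan deals with the correlation between values from the same patient. A between-arm test that ignored it would use too small a standard error and could show one technique retracting faster when neither does. Rate is only a supporting analysis, but it bears on the trial's main question, which technique is quicker. An open unit of analysis can also be settled after the data have been seen.

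**Working it through.** **Inputs from the documents.** Two parallel arms; 10 per group calculated and 15 enrolled (F] Sample size calculation); significance level 0.05, taken as two-sided; visits every 4 weeks.

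**Inputs assumed.** The number of monthly values per patient, m (3 to 8), and the within-patient correlation, ρ (0.1 to 0.5). The documents give neither.

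**1. The plan's own figures.** No error rate is given for the ANOVA beyond the nominal 5%. The sample size reproduces: n = 2 × (1.960 + 0.842)² × 0.76² / 1.0² = 2 × 7.85 × 0.5776 = 9.07, rounded up to 10 per group. It is used here only to fix the arm sizes.

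**2. Monthly values pooled as independent, between-arm test.** With equal correlation between all values of a patient, the true variance of the arm difference exceeds the assumed one by the design effect 1 + (m − 1)ρ. The actual error is therefore

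α = 2 × [1 − Φ(1.96 / √(1 + (m − 1)ρ))].

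Example, m = 6 and ρ = 0.3: design effect 1 + 5 × 0.3 = 2.5; 1.96 / √2.5 = 1.24; α = 21.5%.

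| m | ρ = 0.1 | ρ = 0.3 | ρ = 0.5 |
|---|---|---|---|
| 3 | 7.4% | 12.1% | 16.6% |
| 4 | 8.6% | 15.5% | 21.5% |
| 6 | 11.0% | 21.5% | 29.5% |
| 8 | 13.3% | 26.6% | 35.6% |

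Simulation with 15 per arm and 10,000 trials per setting agrees: 7.3% (m = 3, ρ = 0.1), 21.8% (m = 6, ρ = 0.3) and 35.6% (m = 8, ρ = 0.5).

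**3. What it takes to pass 20%.** The design effect must exceed (1.96 / 1.2816)² = 2.34, so ρ must exceed 1.34 / (m − 1): 0.67 for m = 3, 0.45 for m = 4, 0.27 for m = 6, 0.19 for m = 8. It cannot happen with m = 2.

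**4. Naive test of time or arm-by-time.** Here the patient effect cancels from the numerator but stays in the error term, so the test is conservative. Simulated error with 15 per arm and m = 6 is 0.8% (time) and 0.9% (arm-by-time) at ρ = 0.3, and about 0.1% for both at ρ = 0.5. The cost is power rather than false positives.

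**5. Classical repeated-measures ANOVA.** This needs the same visits for every patient. Follow-up for rate ends at space closure, so patients who close early have no later values. A complete-case analysis removes them, which selects patients on the primary outcome.

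**6. One value per patient.** Simulated error is 4.5–5.6% across all settings, with 10 or 15 per arm. With two groups, F = t², so the ANOVA is the independent-samples t-test.

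**The case against.** A reader might infer that a plain one-way ANOVA is planned, that monthly values will be treated as independent, and that the false-positive rate will exceed 20%. The documents do not support that:

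- Nothing calls the ANOVA plain or one-way, and nothing says the monthly values are treated as independent.
- The statements under Retraction records and D] Outcomes fit one rate per patient, for which the test is valid.
- The monthly models have another stated purpose, the primary duration outcome, so sending them to the statistician does not show that they enter the ANOVA.
- Item 3 names no arms. If it tests change over months, the error falls below 5%.
- Exceeding 20% depends on assumed visit counts as well as assumed correlations. In the table above, 5 of 12 cells do so, none of them at ρ = 0.1. Equal correlation is a further assumption: if the values are monthly increments, adjacent increments share a model, and measurement error pulls their correlation down.

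All of this stands. It is also too broad to say that ANOVA cannot take unequal numbers of visits: one-way ANOVA can, and the limitation belongs to the classical repeated-measures form. Nor would a merely late visit remove a patient, since it still supplies a value.

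What remains is that the line can be read in several ways, only some of them valid, and the plan does not choose.

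**Conclusion.** The point holds as under-specification. The plan names an ANOVA for rate without its type or unit of analysis, although the measurements repeat within patients and their number varies with time to closure. If monthly values are pooled in a between-arm test, the error is above the nominal 5% at any positive correlation; the ranges in the table rest on assumed m, assumed ρ, equal correlation and equal visits. If time effects are tested naively, the test is conservative. If one T0-to-T1 rate per patient is meant, there is no error to correct, only a t-test under another name that leaves the interim models unused for rate.

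A figure above 20% is possible, but it should not be read as the plan's expected error rate. The matter concerns a supporting analysis; the primary duration test and the sample size are untouched. It should be settled before the data are analysed.

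**What to change.** Replace item 3 with one of the following.

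- **Simpler:** fit a least-squares slope (mm per month) to each patient's own models and compare the slopes between arms with an independent-samples t-test. This gives one value per patient and accepts different numbers of visits.
- **Fuller:** a linear mixed model of monthly anterior position on time, arm and arm-by-time, with a patient random intercept and slope. The arm-by-time term is the difference in rate, and unequal follow-up needs no deletion of patients.

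One matter must be settled first. D] Outcomes sets T0 at the start of retraction, but the Clinical Procedure takes the two-step group's pre-intervention records only once canine retraction is finished, while the en-masse group's are taken before any retraction. As written, the two slopes would cover different phases of treatment. If canine retraction is included, a single straight line may not describe incisor position in that arm. These passages need to be reconciled and the period for the slope stated for each arm.

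The cost is a sentence or two in the statistical section plus a common definition of T0. The mixed model is available in SPSS through MIXED. The change of method needs no new measurements; whether the existing model schedule covers the chosen start point in both arms should be confirmed when T0 is settled.
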